of patients who otherwise would not benefit due to the early administration requirement for tranexamic acid. The results provided by the successful completion of this proposal will have paramount implications for both civilian and military injured patients as control of coagulopathy and hemorrhage and delay to definitive care represent major impediments. The current proposal will add needed understanding and insight into improving outcomes when these impediments exist and will promote focus on the mechanisms responsible and the dosing requirements of tranexamic acid that maximize its benefit.

CLINICAL PROTOCOL

A. Statement of Work

Principal Investigators (PIs): [name] and [name] will oversee all planning and execution of the Study of Tranexamic acid during Air Medical Prehospital transport (STAAMP) trial which is a 3 year, multi-center, randomized, double blinded, placebo controlled clinical trial. For patients at risk of bleeding who are transported by emergency medical transport, a 1 gram bolus of prehospital tranexamic acid and subsequent in hospital tranexamic acid dosing regimens will be compared to placebo for clinical, coagulation, inflammatory and dosing regimen endpoints.

Coordinating Center: The University of Pittsburgh will be both the clinical outcome and data coordinating center. The University of Pittsburgh under the auspices of the Principal Investigators will be responsible for the education and training of participating center research staff and will oversee education and training of prehospital providers and research staff for participating centers. The University of Pittsburgh under the auspices of the Principal Investigators will be responsible for sample acquisition, sample storage, data acquisition and entry via web based platform, and maintenance of data integrity.

Participating Centers: Site Investigators from participating centers will oversee the planning and execution of the trial at their respective centers.

The Principal Investigators, the University of Pittsburgh and participating centers will thru the execution of the trial:

1. Determine whether prehospital tranexamic acid as compared to placebo reduces 30 day mortality, reduces the incidence of hyperfibrinolysis, Acute Traumatic Coagulopathy and improves early markers of coagulopathy and hyperfibrinolysis. (r-TEG parameters, D-dimers, activated protein C, and plasmin-anti-plasmin complexes)

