E.1. Study Rationale: Traumatic injured patients continue to be plagued with uncontrolled hemorrhage resulting in significant morbidity and early mortality. A primary driving force for this unbridled hemorrhage is known to be the early coagulopathy which complicates severe injury. Trauma induced coagulopathy has been postulated to be an equilibrium imbalance between pro and anticoagulant factors, platelets, endothelium and fibrinolysis soon after injury. Recent evidence demonstrates that the early use of the antifibrinolytic agent tranexamic acid after trauma center arrival results in improved survival in patients at risk for bleeding. Bringing this proven treatment to the prehospital arena and intervening earlier in those patients who would otherwise not be candidates for treatment has the real potential to further reduce or prevent the vicious hemorrhagic cascade, improve clinical outcomes and provide insight into the underlying mechanisms responsible for and which maximize its benefit.

E.2. Primary Objective: To determine the effect of prehospital tranexamic acid infusion (1 gram over approximately 10 minutes) as compared to placebo during emergency medical transport in patients at risk of traumatic hemorrhage on 30 day mortality.

E.2.1. Primary Aim#1: Determine whether prehospital tranexamic acid as compared to placebo reduces 30 day mortality in patients at risk for traumatic hemorrhage.

Primary Hypothesis 1: Prehospital tranexamic acid as compared to placebo will reduce 30 day mortality in patients at risk of traumatic hemorrhage

E.3. Secondary Objectives: To determine the effect of prehospital tranexamic acid infusion (1 gram over approximately 10 minutes) as compared to placebo during emergency medical transport in patients at risk of traumatic hemorrhage on the incidence of hyperfibrinolysis (estimated percent lysis > 7.5%, first 30 minutes by rapid-thromboelastography) acute traumatic coagulopathy (ATC), early markers of coagulopathy, the incidence of 24 hour mortality, acute lung injury, multiple organ failure and development of nosocomial infection, shock parameters and resuscitation/transfusion requirements, platelet and leukocyte activation and the early inflammatory response and to determine whether different dosing regimens of tranexamic acid upon arrival in the hospital are associated with improvements in hyperfibrinolysis, coagulopathy, clinical outcomes and the early inflammatory response.

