Despite the significant advances in trauma care delivery and post-injury management practices which have occurred over the last decade, uncontrolled hemorrhage remains one of the leading causes of trauma related deaths.^{4,5,87,88} Recent evidence demonstrates that the early use of the antifibrinolytic agent tranexamic acid after trauma center arrival results in improved survival in patients at risk for bleeding.⁴¹ Bringing this proven treatment to the prehospital arena and intervening earlier in those patients who would otherwise not be candidates for treatment has the real potential to further reduce or prevent the vicious hemorrhagic cascade, improve clinical outcomes and provide insight into the underlying mechanisms responsible for and which maximize its benefit. This potential knowledge base would be dramatically beneficial to both military and civilian trauma systems. It is in both these settings where the prehospital phase of treatment represents a relatively novel arena for new interventions. The results provided by the successful completion of this proposal will have paramount implications for both military and civilian injured patients as control of hemorrhage and delay to definitive care represent major impediments for both populations. This proposal will provide needed insight into the consequences of early tranexamic acid intervention in these significantly injured patients when these impediments exist.

H. Research Design and Methods

H.1. Study Design/Setting: The study will be a 3 year, multi-center, blinded, randomized trial utilizing level-1 trauma centers with busy emergency medical transport services with a clinical research track record. For patients at risk of hemorrhage being transported by emergency medical transport, the infusion of 1 gram of tranexamic acid over approximately 10 minutes in the prehospital setting will be compared to placebo. The University of Pittsburgh Medical Center (UPMC) will be both the clinical outcome and data coordinating center. Each individual institution will perform point of care rapid TEG analysis and coagulation measurements on site. UPMC presbyterian is the busiest level-1 trauma center in the state of Pennsylvania and is affiliated with the largest non-profit air medical service in the country with an extensive track record of multi-center, in-

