i. At scene of injury or during emergency medical transport

ii. Documented at referring hospital prior to emergency medical transport arrival

H.2.2 Specific Exclusion Criteria:

1. Age > 90 or < 18 years of age; **2.** Inability to obtain intravenous or intraosseous access;**3.**

Documented (radiographic evidence) cervical cord injury with motor deficit; **4.** Known prisoner; **5.**

Known pregnancy; **6.** Traumatic arrest with > 5 minutes CPR without return of vital signs; **7.**

Penetrating cranial injury **8.** Traumatic brain injury with brain matter exposed; **9.** Isolated drowning or

hanging victims **10.** Wearing an opt out bracelet. **11.** Objection to study voiced by subject or family

member at the scene. **12.** Isolated fall from standing

Inclusion and exclusion criteria will be assessed based on available information at the time of enrollment. Although all reasonable efforts will be made by the emergency medical crew to either directly witness or obtain documentation of inclusion criteria, including qualifying vitals, due to the nature of the emergency pre-hospital setting, there may be occasions where the emergency medical crew must rely on verbal report of qualifying vitals from the referring hospital or ground crew. In these instances, if, after subsequent review of outside hospital and/or ground crew documentation, it is determined that the subject did not meet inclusion criteria

and/or met exclusion criteria, the subject will remain enrolled in the study based on the intention-to-treat principle.

In the event that a verbal report must be used in lieu of physical documentation or directly witnessing the qualifying vitals, documentation of the verbal report will serve as the source documentation for determining eligibility. Verbal reports will be documented in the emergency medical record and will detail the information reported and by whom.

H.3. Interventional Arm: The Intervention will have both a prehospital phase and in-hospital phase. Investigational Drug Services (IDS) at the University of Pittsburgh will be utilized to supply and organize both tranexamic acid and placebo along with respective normal saline bolus and infusion bags to all participating trial sites. IDS at the University of Pittsburgh has a long track record of managing large multicenter trials and is currently executing and responsible for over 150 inpatient and outpatient clinical trials.

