H.3.1. Prehospital Phase Intervention: Once inclusion and exclusion are verified while the patient is being transported via emergency medical transport to a STAAMP trial participating center, in a randomized, double blinded fashion, either 1 gram bolus of tranexamic acid diluted in 100cc of normal saline (pre-prepared on emergency vehicle) or placebo of identical volume will be infused intravenously or intraosseously (if IO access was obtained due to a clinical need per standard of care) into the patient over approximately 10 minutes (“Bag A”). After receiving the prehospital phase intervention, standard operating procedures utilizing goal directed crystalloid infusion will be followed (see **H.7. Prehospital Standard Operating Procedures** below)

H.3.2. In-hospital Phase Intervention: Upon arrival, patient blood and labs will be sampled and arrival rapid-TEG analysis will be performed within first 6 hours. After inclusion and exclusion criteria verification by research staff, in a double blinded, randomized fashion, those patients who received tranexamic acid in the prehospital phase will receive 1 of 3 different dosage regimens:

1. Standard Tranexamic acid Dosing: 1 gram infusion over approximately 8 hours
2. Repeat Tranexamic acid Dosing: 1 gram bolus **and** 1 gram infusion over approximately 8 hours
3. Abbreviated Tranexamic acid Dosing: No further tranexamic acid to be given

For intervention blinding purposes, each patient will receive both a bolus dose (either tranexamic acid or placebo), “Bag B,” and 8 hour infusion (either tranexamic acid or placebo), “Bag C,” depending on the randomized dosing regimen. (Figure 13. below)

H.3.2.1 Adjustment For Renal Insufficiency: Subjects with a known or suspected history of renal insufficiency will receive a renal dose adjustment for the 8 hour repeat infusion (Bag C). The Estimated Body Weight Table will be used to determine the dose (Figure 12). The dose will be capped at 1000 mg.

1. Standard Dosing: bolus- no dose adjustment / infusion- 1.25 mg/kg/hr x 8hrs
2. Repeat Dosing: bolus- no dose adjustment / infusion- 1.25 mg/kg/hr x 8hrs
3. Abbreviated Dosing: bolus- no dose adjustment / infusion- 1.25 mg/kg/hr x 8hrs

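### Sections E.2 and H.1 ask about the 1 g prehospital infusion, but the primary mortality comparison estimates a prehospital-started TXA strategy averaged over three in-hospital regimens

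*Combined protocol and SAP*

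**What the plan says.** Section E.2 (Primary Objective) asks for the effect of one treatment component: "To determine the effect of prehospital tranexamic acid infusion (1 gram over approximately 10 minutes) as compared to placebo", on 30-day mortality. Section H.1 describes the trial in the same way: "the infusion of 1 gram of tranexamic acid over approximately 10 minutes in the prehospital setting will be compared to placebo".

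Other sections describe something wider. The Statement of Work (section A) says that "prehospital tranexamic acid and subsequent in hospital tranexamic acid dosing regimens will be compared to placebo". Section H.3 opens with "The Intervention will have both a prehospital phase and in-hospital phase". Under H.3.2, "those patients who received tranexamic acid in the prehospital phase will receive 1 of 3 different dosage regimens": standard (1 g more), repeat (2 g more), or abbreviated, defined as "Abbreviated Tranexamic acid Dosing: No further tranexamic acid to be given". Under H.4 the prehospital placebo arm receives only placebo in hospital.

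Sections J and J.1.1 group all randomised patients by prehospital assignment and test 30-day mortality with a Mantel-Haenszel test stratified by site. In-hospital regimen does not enter. Section J.3 plans a chi-square test and a trend test for the dosage regimens. Hypothesis 4B (section E.3.4) expects repeat dosing to lower 30-day mortality relative to the other two regimens.

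**The concern.** The question in E.2 and the contrast in J.1.1 are different. The active arm gets the prehospital gram and then, for most patients, more TXA; the control arm gets no trial TXA at any stage. The primary result mixes the effect of the prehospital gram with the average effect of what follows. The two coincide only if in-hospital dosing has no net effect on mortality, and Hypothesis 4B assumes that dose does matter.

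A positive result reported in E.2's words could therefore credit the prehospital gram with benefit that comes partly, or wholly, from in-hospital dosing. The contrast that isolates the gram is abbreviated dosing versus placebo, and no section plans it.

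**Working it through.** **Inputs from the plan.** Control mortality 16% and 497 per arm (K.1); alternative 10% versus 16% (P.4); pooled-variance z test, two-sided alpha 0.05 (K.1); block size 9 for three regimens (H.5.2).

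**Assumptions.** 1:1:1 allocation, which block size 9 suggests but the plan does not state. All mortality patterns below other than 16% and the 10% average are illustrations. Interim looks are ignored.

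**1. The plan's own figures.** For 0.0919, 0.0965 and 0.1003 versus 0.16 with 497 per arm, power is 0.900, 0.851 and 0.800, matching the K.1 table. For 0.10 versus 0.16:

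- SE under the null = √(2 × 0.13 × 0.87 / 497) = 0.02133
- SE under the alternative = √((0.10 × 0.90 + 0.16 × 0.84) / 497) = 0.02125
- Power = Φ((0.06 − 1.96 × 0.02133) / 0.02125) = Φ(0.856) = 0.804

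These hold for the pooled arm, whatever the estimand is called.

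**2. How much of the TXA arm gets more TXA.** 497 × 2/3 = 331 patients. If 5% or 10% never reach stage 2 (assumed), 315 or 298. With full entry and no renal adjustment, assigned TXA averages (1 + 2 + 3)/3 = 2 g, against 0 g in the control arm.

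**3. The pooled contrast cannot identify the gram's effect.** Placebo 16%:

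| Abbreviated / standard / repeat | Pooled mean | Pooled difference | Effect of the gram alone |
|---|---|---|---|
| 10 / 10 / 10% | 10% | −6 points | −6 points |
| 13 / 10 / 7% | 10% | −6 points | −3 points |
| 16 / 7 / 7% | 10% | −6 points | 0 |
| 10 / 13 / 13% | 12% | −4 points | −6 points |

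The first three rows have the same primary power, 0.804. The fourth shows that the error can also run the other way.

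**4. Whether J.3 would give warning.** Trials were simulated (400,000 per scenario) with regimens of 166, 166 and 165 patients. The entries are the share of positive primary results in which the J.3 test is not significant. Flat means that 1 g and 2 g extra have equal effect (2-df chi-square); graded means linear in extra dose (trend test).

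| Pooled TXA mortality | Primary positive | Gram gives 0: flat / graded | Gram gives half: flat / graded |
|---|---|---|---|
| 14% | 0.14 | 89% / 83% | 94% / 92% |
| 12% | 0.44 | 64% / 41% | 88% / 81% |
| 10% | 0.80 | 22% / 4% | 74% / 57% |

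If either J.3 test counts as detection, the 10% row becomes 17% / 3% (gram gives 0) and 67% / 54% (gram gives half).

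**5. The contrast that answers E.2 as worded.** Abbreviated (166) versus placebo (497), 10% versus 16%:

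- 95% half-width = 1.96 × √(0.10 × 0.90/166 + 0.16 × 0.84/497) = 5.6 points, against 4.2 for the pooled contrast
- Power (pooled z) = 0.47; the smallest difference detectable with 80% power is about 8.3 points

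**6. Patients who die or leave before stage 2.** Stage 2 is allocated only after arrival (H.5.2), so setting abbreviated patients directly against all placebo patients leaves out TXA patients who never got that far. Take true mortality of 16% in both arms and 50% mortality among non-entrants (assumed):

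- 5% non-entry: (0.16 − 0.05 × 0.50)/0.95 = 14.2%, a false benefit of 1.8 points
- 10% non-entry: (0.16 − 0.10 × 0.50)/0.90 = 12.2%, a false benefit of 3.8 points

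Keeping non-entrants at weight 1 and weighting abbreviated patients by 3 removes this. With 5–10% non-entry and 10–50% of them dying (assumed), the half-width is 5.0 to 5.5 points.

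**7. A related inconsistency.** H.3.2 defines abbreviated dosing as no further TXA, yet H.3.2.1 lists "Abbreviated Dosing: bolus- no dose adjustment / infusion- 1.25 mg/kg/hr x 8hrs". Because every patient gets both in-hospital bags for blinding, this may be only the matched setting for the blinded infusion bag. The text does not say so, and this is the one regimen that isolates the prehospital gram.

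**The case against.** The strategy is openly disclosed: the synopsis, the Statement of Work, H.3, H.4 and H.5.2 all set out the two stages. Section E.2.1 and Primary Hypothesis 1 name prehospital TXA without a dose, and an intention-to-treat effect of prehospital assignment with its protocolised later care is a normal reading of that aim. No stated hypothesis asks for abbreviated versus placebo, and at 47% power it would settle little. Most of the simulated figures rest on assumed response patterns. The highest missed shares belong to a 2-point effect that the primary would rarely detect. At the plan's own 6-point effect with no contribution from the gram, J.3 misses only 22% or 4%. Where the gram supplies half, E.2's conclusion is right in direction and wrong only in size.

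Much of this is fair. The test, the sample size and the analysis set are sound, and J.3 gives useful warning in some cases. But disclosure elsewhere makes the documents inconsistent; it does not resolve which question the primary answers. Abbreviated versus placebo is the contrast that E.2's wording calls for, so asking to see it estimated is not just a preference. Low power is a reason to report it as an interval without a claim. The 1.8- and 3.8-point biases are not a flaw in any planned analysis; they show why the added contrast must be done with weights.

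**Conclusion.** The concern holds. It is a mismatch between the stated question and the estimand, not an error in the test or in the 994 total. With 1:1:1 allocation and full stage-2 entry, two thirds of the TXA arm is assigned TXA beyond the dose named in E.2. A 6-point pooled difference is compatible with the prehospital gram contributing all, half or none of it. J.3 can show that in-hospital dose matters, with a chance that depends on the size and shape of the response, but it never estimates the gram against placebo. The mismatch follows from the text alone; the sizes rest on the inferred allocation ratio and on illustrative mortality and non-entry rates. It should be corrected before results are reported.

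**What to change.** 1. Align E.2, E.2.1, H.1 and J with the Statement of Work: the primary estimand is the prehospital-started TXA strategy, averaged over the three in-hospital regimens, versus no trial TXA.
2. Pre-specify abbreviated dosing versus placebo as a supportive, site-stratified risk difference in 30-day mortality with a 95% confidence interval. Keep TXA patients who never reach stage 2 at weight 1, weight abbreviated patients by the inverse of their allocation probability (3 if 1:1:1), and use a variance that reflects the weights. State the stage-2 ratio. Make no claim about the prehospital gram alone from the pooled contrast.
3. Reconcile the definition of abbreviated dosing in H.3.2 with its infusion entry in H.3.2.1. If the entry is only the blinded bag setting, say so.

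The cost is wording, one supportive analysis and one clarification; the sample size and primary test are untouched. The price is a narrower headline claim and an imprecise estimate for the prehospital gram alone.
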